Study Objective(s)	
The primary objective of this study is:
 
 • To demonstrate a significant improvement of Palmoplantar Pustulosis Psoriasis Area and Severity Index (PPPASI) at week 20 compared with baseline in moderate to severe chronic palmoplantar pustulosis under apremilast therapy. 
The secondary objectives of the study are:
 
 • To evaluate an improvement of PPPASI at all assessment times compared with baseline in moderate to severe chronic palmoplantar pustulosis under apremilast therapy. • To evaluate differences during the treatment with apremilast in life quality assessment measures: Dermatology Life Quality Index (DLQI) at all assessment times compared with baseline • To evaluate safety of apremilast in patients with moderate to severe palmoplantar pustulosis 
Exploratory objectives are:
 
 • Time course of Hand and Feet Physician Global Assessment (H&F PGA) at all assessment times. • Pustules count 50 response and Pustules count 75 response, defined as a 50% and 75% decrease in Pustules count from baseline, during the 20 weeks treatment period • To evaluate differences in the mean change from baseline at all assessment times of Visual Analogue Scale (VAS) discomfort / pain, VAS pruritus / itch at all assessment times relatively to day 0 (baseline) • To evaluate changes in Psoriasis Area Severity Index (PASI), Physician Global Assessment (PGA) and dynamic PGA if plaque psoriasis is present between baseline and all assessment times • To explore the effect of apremilast on serum / plasma immunological markers • To explore the effect of apremilast on immunological markers in skin biopsy samples (sub-study)
Approximate Duration of Study	The study is estimated to have duration of approximately 11 months from first patient in (FPI) to last patient out (LPO). Enrolment will cease if the target number of patients is reached.

Duration of Patient Participation	Up to 4 weeks screening period, 20 weeks treatment period
Number of Visits	5
Approx. Number of Sites	5 in Germany
Number of Patients	20
Target Disease	Palmoplantar pustulosis (PPP)
Criteria for Inclusion	
 • Male and female patients aged 18 years or more at screening visit. • Patients with chronic PPP (disease history of at least 6 months of diagnosis), who are eligible for treatment with systemic therapy defined as having PPP inadequately controlled by topical treatment and / or phototherapy and / or previous systemic therapy • Patients with chronic moderate to severe PPP defined as patients with a PPPASI ≥ 12 with or without concomitant plaque-type psoriasis • Negative result of a urine pregnancy test taken at screening and at baseline for all women, except those who are surgically sterile or at least 1 year postmenopausal (i.e. at least 12 consecutive months with amenorrhea without other known or suspected medical cause) • Willingness and capability of using a highly effective contraceptive measure from Screening visit until the end of at least one menstrual cycle (but not less than 28 days) following discontinuation of apremilast as defined below: 
 ○ Female patient of childbearing potential (fertile, following menarche and until becoming post-menopausal unless permanently sterile) using a highly effective method of contraception OR female patients of non-childbearing potential (surgically sterilized [e.g. hysterectomy, bilateral salpingectomy and bilateral oophorectomy] or post-menopausal) ○ Male patient, and his female partner of childbearing potential, using a highly effective method of contraception ○ Adequate contraceptive method defined as: 
 ▪ A method with less than 1% failure rate (e.g. permanent sterilization, hormone implants, hormone injections, some intrauterine devices, or vasectomized partner) 
OR
 
 ▪ The use of two methods of contraception (e.g. one barrier method [condom, diaphragm or cervical/vault caps] with spermicide and one hormonal contraceptive [e.g. combined oral contraceptives, patch, vaginal ring, injectables and implants]) 
 • Patient is capable of understanding and giving written, voluntary informed consent before study screening. • Willingness and capability of complying with all study procedure requirements, as per the Investigator's judgment

	(e.g. patient able to swallow the apremilast tablets, blood sampling).
Criteria for Exclusion	
General
 
 • Pregnant or breast-feeding women • Current or history of psychiatric disease that would interfere with the ability to comply with the study protocol or give informed consent • Patients known to have had a substance abuse (drug or alcohol) problem within the previous 12 months • Individuals who are involved in the organization of the study • Patients who are in any way dependent on the investigator • Patients who are participating in a clinical study • Relatives, partner or staff of any clinical site personnel 
Disease-related
 
 • Evidence of skin conditions (e.g. eczema) other than PPP / psoriasis that would interfere with evaluations of the effect of study medication on PPP or psoriasis. • Laboratory values available from routine blood test taken within 8 weeks prior to screening with any of the following: 
 ○ Serum creatinine $>1.4 \times$ upper limit of normal (ULN) for age and gender ○ Estimated Glomerular Filtration Rate (eGFR) $< 30 \text{ mL/min}/1.73 \text{ m}^2$ according to the CKD-EPI equation • Pustular psoriasis lesions on the part of body other than hands or feet • Significant concurrent medical conditions at the time of screening, including: 
 ○ Risk factors for renal toxicity (renal inflammation) ○ Severe hepatic dysfunction ○ Unstable angina pectoris ○ Uncompensated congestive heart failure ○ Severe pulmonary disease requiring hospitalization or supplemental oxygen therapy ○ Immunodeficiency disorders: primary or secondary ○ Known positive HIV test result, hepatitis B surface (HBS) antigen or hepatitis C (HCV) test result ○ Uncontrolled Insulin-dependent diabetes mellitus ○ Cancer or history of cancer (except for resected cutaneous basal cell or squamous cell carcinoma) in the last 5 years ○ Open cutaneous ulcers • Any condition that, in the judgment of the investigator, might cause this study to be detrimental to the patient. 
Medication-related
 
 • Ultraviolet B (UVB) therapy, topical steroids, topical calcineurin inhibitors, topical Vitamin A or D analog preparations, or anthralin within 14 days of baseline • Exceptions: low potency topical corticosteroids (class I and II, according to European classification for potency of topical corticosteroids) will be allowed as therapy for the face, groin, axillae in accordance with the manufacturer's suggested usage dose

	
 Psoralen plus ultraviolet A radiation (PUVA), ciclosporin, acitretin, alitretinoin, alefacept (Amevive[®]), anakinra (Kineret[®]), systemic corticosteroids, methotrexate, fumaric acids or any other systemic anti-psoriasis therapy within 28 days of baseline Prior (within the last 2 years) or concomitant use of antipsoriatic biologic therapy with Tumor Necrosis Factor (TNF)-α blocker and / or ustekinumab and / or ixekizumab and / or secukinumab and / or brodalumab and / or guselkumab Concomitant use of strong cytochrome P450 3A4 (CYP3A4) enzyme inducers (e.g. rifampicin, phenobarbital, carbamazepin, phenytoin and St. John's wort) Use of an investigational drug within 4 weeks prior to baseline or 5 pharmacokinetic / pharmacodynamics half-lives (whichever is longer) Prior treatment with apremilast / Otezla[®] Receipt of any live (attenuated) vaccine within 28 days prior to baseline. Concomitant use of any other phosphodiesterase 4 inhibitor Patients with hereditary problems of galactose intolerance, lapp lactase deficiency or glucose-galactose malabsorption For patients with skin biopsy samples taken: patients with clinically relevant coagulation disorders or medication or known hypersensitivity against local anesthetics
Investigational Medicinal Product (Including Placebo and Active Comparator, If Any)	Apremilast (Otezla [®])
Dosage and Administration	Apremilast BID, orally Day 1: 10 mg in morning Day 2: 10 mg in morning and 10 mg in evening Day 3: 10 mg in morning and 20 mg in evening Day 4: 20 mg in morning and 20 mg in evening Day 5: 20 mg in morning and 30 mg in evening Day 6 and thereafter: 30 mg twice daily
Concomitant Treatment	Required concomitant medication (except those listed under exclusion criteria) for the treatment of concomitant diseases and not known to interfere with the study drug or to mask the effect of the study drug, is unrestricted and may be continued during the study. Low potency topical corticosteroids (class I and II, according to European classification for potency of topical corticosteroids) will be allowed as background therapy for the treatment of the face, axillae, and groin in accordance with the manufacturer's suggested usage during the course of the study except for lesions selected for clinical evaluations. An unmedicated skin moisturizer (without urea) is permitted for body lesions only. Patients should not use the unmedicated skin moisturizer within 12 hours prior to the clinic visit on lesions selected for clinical evaluations.

Efficacy Evaluation	Efficacy will be assessed by evaluating PASI, PPPASI, PGA, dynamic PGA, H&F PGA, pustules count, VAS for pruritus / itch and discomfort / pain on hands and feet, DLQI, and immunological markers.
Safety and Tolerability Evaluation	Safety will be assessed by evaluating Adverse Events (AEs), vital signs and physical examination.
Primary Endpoint	Percentage change from baseline in PPPASI after 20 weeks of treatment with apremilast
Secondary Endpoints	
 Absolute and percent change from baseline in PPPASI during the 20 weeks treatment period PPPASI 50 response and PPPASI 75 response, defined as a 50% and 75% decrease in PPPASI from baseline, during the 20 weeks treatment period DLQI bands (0-1 no effect, 2-5 small effect, 6-10 moderate effect, 11-20 very large effect, 21-30 extremely large effect on the disease related quality of life) during the 20 weeks treatment period Absolute and percent change from baseline in DLQI during the 20 weeks treatment period Safety as assessed by AEs, vital signs and physical examination
Exploratory Endpoints	
 Absolute and percentage change from baseline in level of immunological markers in plasma / serum during the 20 weeks treatment period with apremilast Percentage change from baseline in level of immunological markers in skin biopsy samples after 20 weeks of treatment with apremilast (sub-study)
Data Analysis / Statistical Methods	
This is a pilot study intended to gain first information on the possible clinical and mechanistical effects of apremilast on PPP; therefore the sample size is not based on statistical considerations.
 
The Full Analysis Set (FAS) is defined as all patients who received at least one dose of study drug and the Per Protocol Set (PP) is defined as all patients who received at least one dose of study drug who completed the study with no major protocol violations. These two analysis sets will be used for analyses of efficacy endpoints. The definition of the PP set will be finalized in the data review meeting prior to database closure.
 
In general, categorical variables will be summarized using frequencies and percentages and continuous variables will be summarized using number of observations, mean, standard deviation, median, minimum, first quartile, third quartile, and maximum.
 
The primary endpoint percent change from baseline in PPPASI after 20 weeks of treatment will be summarized as continuous variable together with 95%-confidence limits. Statistical comparison between post- versus pre-treatment values will be done based on the Wilcoxon signed-rank test with two-sided p-value <0.05 indicating significance. Missing values will be replaced

	
using last-observation-carried-forward (LOCF) method for the analysis of the primary endpoint based on the FAS. Exploratory endpoints (plasma / serum immunological marker analysis and the skin biopsy immunological marker (sub-study)) will be analyzed outside of the study setting by a research laboratory (Psoriasis Research and Treatment Center, University Hospital Charité, Berlin, Germany). Statistical comparison between post-versus pre-treatment values will be done based on the Wilcoxon signed-rank test with two-sided p-value <0.05 indicating significance.

Ethical Considerations	
This study will be conducted in accordance with applicable laws and regulations including, but not limited to, the ICH E6 guideline and the ethics principles that have their origins in the Declaration of Helsinki. The independent ethics committee and the competent authority must review and approve the study before any patients are enrolled. Consent must be obtained from the patient using the approved informed consent form (ICF) before any procedures specified in the protocol are performed.
 
The data acquisition meets all requirements of data protection for each individual patient, since all patient-related documentation can only be identified by a patient identification number. All personal information of the patient is accessible only to the treating physician.

Study Flow Chart

Phase	Screening	Treatment Phase					Early Termination
		V2 Baseline	V3	V4	V5 End of Study		
Visits	V1						
Week	-4 -- 1	0	4	12	20		
Day	-28 -- 1	0	28 ± 4	84 ± 4	140 ± 7		
In- / exclusion criteria	x	x	-	-	-	-	-
Pregnancy test ¹	x	x	x	x	x	x	
Informed consent	x	-	-	-	-	-	
Demography, educational status	x	-	-	-	-	-	
Medical and psoriasis history, prior medication	x	-	-	-	-	-	
PsA, comorbidity	x	x	-	x	x	x	
Concomitant medications	x	x	x	x	x	x	
Nicotine anamnesis	x	-	-	-	x	-	
Physical examination incl. weight and height ² (BMI)	x	x	-	-	x	x	
Vital signs ³	x	x	x	x	x	x	
Results of routine blood test / urinalysis available ⁴	x	-	-	-	-	-	
Investigator assessments							
PASI	-	x	x	x	x	x	
PPPASI	x ⁵	x	x	x	x	x	
PGA	-	x	x	x	x	x	
H&F PGA	-	x	x	x	x	x	
Dynamic H&F PGA	-		x	x	x	x	
Pustules count	-	x	x	x	x	x	
Patient reported outcomes							
VAS (pruritus / itch and discomfort / pain) on hands and feet	-	x	x	x	x	x	
DLQI	-	x	-	x	x	-	
Photographs ⁶ (optional)	-	x	-	-	x	-	
Serum and plasma	-	x	x	x	x	x	
Biopsies ⁷ (optional sub-study)	-	x	-	-	x	x	
Documentation for drug accountability and treatment compliance	-	x	x	x	x	x	
Medication dispensing ⁸	-	x	x	x	-	-	
Return of study medication	-	-	x	x	x	x	
AEs / SAEs	x	x	x	x	x	x	
Reason for discontinuation						x	

1. Urine pregnancy test for female patients of childbearing potential
2. Only at V1: height
3. Sitting blood pressure and pulse rate
4. Within the ranges given in the exclusion criteria **not older than 8 weeks** prior to screening
5. For inclusion PPPASI must be ≥ 12
6. From both hands and feet (optional)
7. Two lesional biopsies from feet or hands (optional)
8. Including instructions for medication intake

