6.2 Potential Risks and Benefits

According to the 'summary of the risk management plan (RMP) for Otezla® (apremilast)' (29), by blocking the action of PDE4, apremilast reduces the symptoms of psoriasis and psoriasis arthritis. Because of exclusion of patients with moderate / severe kidney disorders, liver disorders, children and pregnant or breastfeeding patients from clinical trials, there is no information on safety or effectiveness of Otezla® for these patients. However, these patient groups will also be excluded for the clinical study presented here.

Important identified risks include:

- weight decrease in patients with Body Mass Index (BMI) <20 kg/m²
- depression

Important potential risks include:

- inflammation of blood vessels (vasculitis)
- risk of triggering suicide (suicidal thoughts)
- tumors (malignancies)
- nervousness and anxiety
- serious infections
- major heart problems (major adverse cardiac events [MACE] and tachyarrhythmia)
- effects on the developing child if used during pregnancy

For more detailed information on these identified and potential risks please refer to the 'summary of the risk management plan (RMP) for Otezla® (apremilast)' (29) and the 'Rote Hand Brief' (30).

Otezla® has been approved for the treatment of patients with moderate to severe plaque psoriasis and for the treatment of patients with active psoriatic arthritis. Overall, no serious safety issues are associated with Otezla® and the benefit-risk profile for Otezla® is acceptable and the risks can be mitigated through professional labeling.

7 Study Objectives and Purpose

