11.2.3 Visit 3 - (Week 4, Day 28 ±4)

- A urine pregnancy test (β -hCG) will be performed in females with childbearing potential.
- Vital signs will be assessed.
- Concomitant medication will be documented.
- The patient will be interviewed concerning the occurrence of AEs.
- Serum and plasma samples will be taken.
- The investigator will
 - ask the patient to rate their pruritus and pain on hands and feet using the VAS.
 - assess the PASI, PPPASI, PGA, H&F PGA, dynamic H&F PGA and pustules count.
- Study medication will be collected for drug accountability and documentation for treatment compliance. Further study medication will be dispensed. The patient will be reminded and re-instructed on when and how to take the study medication.
- The patient will be instructed to return all study medication to the next visit.
- A return appointment for the next visit will be scheduled.

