11.2.5 Visit 5 - (Week 20, Day 140 ±7)

- A urine pregnancy test (β -hCG) will be performed in females with childbearing potential.
- Nicotine anamnesis will be documented.
- Physical examination including weight and vital signs will be assessed.
- PsA and comorbidity will be documented.
- Concomitant medication will be documented.
- The patient will be interviewed concerning the occurrence of AEs.
- Serum and plasma samples will be taken.
- The investigator will
 - ask the patient to rate their pruritus and pain on hands and feet using the VAS and to fill in the DLQI questionnaire.
 - assess the PASI, PPPASI, PGA, H&F PGA, dynamic H&F PGA and pustules count.
- Study medication will be collected for drug accountability and documentation for treatment compliance.
- Photographs will be taken (optional).
- Biopsies will be taken (two lesional biopsies from feet or hands). The taking of biopsies is optional.

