6.3.11 Other Safety Assessments

All safety evaluations will be performed on the FAS.

Vital Signs

For all vital signs parameters (systolic and diastolic blood pressure and pulse rate), summary statistics will be provided by visit.

Physical Examination

Height, weight, BMI and numbers of values that are normal or abnormal will be tabulated by visit.

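### Weight loss at BMI below 20 kg/m² is a named risk, but no weight is scheduled at V3 or V4 and the SAP plans no within-patient weight change

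*Protocol*

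**What the plan says.** **The risk.** Protocol 6.2 lists two important identified risks of apremilast: depression, and "weight decrease in patients with Body Mass Index (BMI) <20 kg/m²". The inclusion and exclusion criteria (Protocol 9.1.1 and 9.1.2) contain no BMI limit. Safety is a secondary objective, and physical examination is part of the safety endpoint (Protocol 7.2 and 8.2.2).

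**The schedule.** Weight belongs to the flow-chart row "Physical examination incl. weight and height". That row is marked at V1, V2, V5 and early termination and blank at V3 and V4, in the protocol and in the SAP alike. A footnote adds "Only at V1: height". The visit texts agree. At V3 and V4 (Protocol 11.2.3 and 11.2.4) the entry is "Vital signs will be assessed", and the flow chart defines vital signs as "Sitting blood pressure and pulse rate". At V5 (Protocol 11.2.5) it is "Physical examination including weight and vital signs will be assessed", and early termination (11.2.6) has the same entry.

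**The analysis.** Protocol 14.7 gives summary statistics for each vital sign and physical examination parameter per visit. SAP 6.3.11 says: "Height, weight, BMI and numbers of values that are normal or abnormal will be tabulated by visit". The output is Table 14.3.7, with individual values in Listing 16.2.10. In the SAP's table list, change from baseline appears only for PPPASI and DLQI. No subgroups are planned.

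**The concern.** A named risk of weight loss is a question about change within a patient, and about a particular kind of patient. The plan collects and reports weight in a way that answers neither part directly.

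During treatment, the two scheduled visits at which a weight could inform the investigator do not include one. V5 comes at the end of treatment, and the early termination visit follows the decision to stop.

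In the report, the tables would give the distribution of weight and BMI at each visit. They would not say how much any patient lost, how many lost weight, or how many entered with BMI below 20 kg/m². A reader who wants to know whether the named risk showed itself would have to pair values by hand.

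**Working it through.** The plan states no figure on this point, so there is none to reproduce. The check sets the schedule and the planned outputs side by side, with simple arithmetic.

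**1. Scheduled weights and the interval between them.**

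| Visit | Day | Weight scheduled | Blood pressure and pulse |
|---|---|---|---|
| V1 | -28 to -1 | yes | yes |
| V2 | 0 | yes | yes |
| V3 | 28 ± 4 | no | yes |
| V4 | 84 ± 4 | no | yes |
| V5 | 140 ± 7 | yes | yes |
| Early termination | variable | yes, if the visit takes place | yes |

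For a completer the gap from V2 to V5 is 140 - 7 = 133 to 140 + 7 = 147 days, or 19 to 21 weeks. One of the three scheduled post-baseline visits includes a weight. If V3 and V4 also had one, the nominal gaps would be 28, 84 - 28 = 56 and 140 - 84 = 56 days. At the extremes of the windows, the two longer gaps would be (84 + 4) - (28 - 4) = 64 days and (140 + 7) - (84 - 4) = 67 days.

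**2. What the by-visit table shows.** Take an assumed patient 1.65 m tall with BMI 19.5 kg/m².
- Weight: 19.5 × 1.65² = 53.1 kg.
- A 10% loss is 5.3 kg, leaving 53.1 - 5.3 = 47.8 kg and a BMI of 47.8 / 1.65² = 17.6 kg/m².
- Effect on a mean over all 20 planned patients: 5.3 / 20 = 0.27 kg.

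The mean hardly moves. SAP 6.3.2 also requires minimum, quartiles and maximum, so if this patient is the lightest at both visits the minimum falls from 53.1 to 47.8 kg. The table does not show whether the two minima belong to the same person. A percentage-change column would show -10% directly.

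**3. Drop-outs.** Drop-outs are not replaced (Protocol 8.1), and missing values outside the primary analysis are not imputed (SAP 6.6). The V2 column therefore covers everyone weighed at baseline, and the V5 column only those who reached Week 20.

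**4. How many patients the risk could concern.** The documents do not give the share with BMI below 20 kg/m². For an assumed share p among 20 patients, the expected number is 20p and the chance of at least one is 1 - (1 - p)^20.

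| Assumed share | Expected number | Chance of at least one |
|---|---|---|
| 2% | 0.4 | 33% |
| 5% | 1 | 64% |
| 10% | 2 | 88% |

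Such small numbers favour an individual display over a subgroup table.

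**5. Whether the SAP fix is possible on data already planned.** SAP 6.3.1 defines absolute and percentage change for a generic visit and takes V2 as baseline. Weight is collected at V2, V5 and early termination. Height is taken at V1 only, and SAP 6.3.1 treats V1 as baseline for a variable not measured at V2. Baseline BMI therefore follows from V1 height and V2 weight.

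**The case against.** A reader might infer that a loss on treatment would be neither seen in time nor reported, or that the planned table cannot show it. The documents do not support either statement:
- Adverse events are asked about at every visit, V3 and V4 included (Protocol 13.2). A loss recorded as an event would enter the treatment-emergent tables.
- Protocol 12.2.3 allows extra examinations when symptoms or history call for them, and 11.2.7 allows unscheduled visits.
- A patient who stops early is weighed if the early termination visit takes place.
- Table 14.3.7 reports weight and BMI with their extremes and quartiles, and Listing 16.2.10 holds each patient's values.

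It is also tempting to set the 0.27 kg shift against the standard error of the mean weight. That standard error describes differences between patients, is a poor yardstick for change within the same patients, and needs a standard deviation that the documents do not give.

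Two further points are fair. Section 6.2 promises no weighing during treatment and refers to the risk management plan for details, so there is no outright contradiction. The investigator may also exclude a patient for any condition that makes participation harmful, or withdraw one in the patient's interest.

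All of this stands and sets the limits of the point. What remains is that adverse event reporting and discretionary examination need someone to notice the loss first, and that the answer on a named risk is left to be derived from a listing.

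**Conclusion.** The point holds as a gap in scheduling and display. For completers no weight is scheduled for 133 to 147 days, so detection during treatment rests on adverse event reporting or a discretionary examination. The report will contain the data but no within-patient weight change and no identification of patients with baseline BMI below 20 kg/m². With drop-outs, the V2 and V5 summaries describe different patients.

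The interval and the missing outputs come straight from the documents. The number of patients affected does not: 0.4 to 2 expected rests on an assumed share of 2% to 10%, and the 53.1 kg patient is an illustration. The primary efficacy analysis is not touched.

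**What to change.** **SAP (no new data; low cost).** In SAP 6.3.11 and Table 14.3.7, apply the absolute and percentage change definitions of SAP 6.3.1 to weight, from V2 to V5 and from V2 to early termination. Give the number of patients contributing to each. In Listing 16.2.10, flag patients whose baseline BMI is below 20 kg/m². The documents set no loss categories; if the sponsor wants some, they are descriptive display choices to fix in the SAP before database lock. The cost is one extra table panel and one derived flag.

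**Protocol (small burden; needs an amendment).** The sponsor should reconcile both flow charts and Protocol 11.2.3 and 11.2.4 with the risk named in 6.2. One way is to record weight at V3 and V4 with the vital signs already taken there, which means two more weighings per patient. The downside is a protocol amendment, with ethics and authority approval where required (Protocol 17.3), and a change to the paper CRF. If V3 and V4 weights are added, the change table should include them. No rule for clinical action on a weight loss is proposed here.
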